1. PROTOCOL SUMMARY

The study sponsor has decided to cease enrollment based on a rapidly evolving treatment landscape in urothelial carcinoma, in addition to recent data showing lack of efficacy of bintrafusp alfa in studies in other tumor types.

In line with the sponsor's decision, this protocol has been amended to provide updated instructions for study conduct.

At the time of writing this protocol amendment, 25 participants have been treated with bintrafusp alfa, and no new safety signals were identified.

In summary, participants still on treatment at the time of the final data cut-off (DCO) date and who the study investigator in agreement with the GSK medical monitor considers are deriving benefit from bintrafusp alfa and do not meet any protocol-defined treatment discontinuation criteria may continue to receive study intervention per the protocol-defined time period after the DCO date, as follows:

- Participants who decide to continue with study intervention are re-consented.
- Participants will be managed in accordance with the local institutional standard of care.
- Serious Adverse Events (SAEs), adverse events (AEs) leading to treatment/study discontinuation, overdoses, and pregnancies will be reported through a paper-based pharmacovigilance (PV) process (see Study Reference Manual) and captured in asset PV database.

A DCO date will be specified that represents the end of data collection for the planned final analysis described in the Reporting and Analysis Plan (RAP). The DCO date will be communicated to the study sites in a letter. Once the final DCO for this study has been reached, no new data will be entered into the clinical study database and the database will be locked for final analysis. At the time of final DCO, participants in follow-up will no longer be followed for survival and will be considered to have completed the study. Although the clinical study database(s) will be closed at the time of the final DCO date, the study remains open until all participants discontinue study treatment and the end of study (EOS) is reached. The EOS is defined as the date of the last visit of the last participant in the study.

The reporting of this study will focus on the primary and secondary objectives only.

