[figure not shown]
- During the 45-day Screening period, participants will be evaluated for study eligibility per protocol as defined in the Inclusion/Exclusion criteria. Eligible participants must have confirmed diagnosis of metastatic or locally advanced/unresectable urothelial cancer with disease progression or recurrence following treatment with a platinum agent.
- During the Treatment Period, safety and disease assessments will be performed regularly according to the Schedule of Activities (SoA). Treatment will continue until disease progression as determined by RECIST 1.1, death, unacceptable toxicity, sponsor decision to terminate the study, or other protocol-defined criteria are met, for up to 2 years or up to 2 years from confirmed complete response. Note: participants receiving treatment may continue past PD if the participant's ECOG PS has remained at least stable, and if in the opinion of the investigator and in consultation with the GSK medical monitor, the participant will benefit from continued treatment.
- For participants who discontinue study intervention for reasons other than or in the absence of PD, disease evaluation will continue to be performed until confirmed PD (documented), death, start of a new anti-cancer therapy, or withdrawal of consent. After the DCO date, it is expected that disease evaluation will be performed per institutional practice, but these data will not be collected by the sponsor.
- After study treatment is permanently discontinued, participants will be followed for survival and subsequent anti-cancer therapy once every 12 weeks (Q12W) for a maximum of 3 years from the date of enrollment. At DCO, survival and subsequent anti-cancer therapy in participants in follow-up will no longer be collected by the sponsor and participants will be considered to have exited the study.
- After study treatment is permanently discontinued, all SAEs, nonserious treatment-related AEs, and AEs of interest will be followed until the event is resolved, stabilized, otherwise explained, or the participant is lost to follow-up. Related AE of all other AEs will be followed until the last follow up visit. At the

DCO, participants still receiving study intervention will be followed as outlined in Section 8.2.

Participants who permanently discontinue study treatment will enter the follow-up period of the study and undergo the assessments as described in the SoA until the DCO date.

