1.3. Schedule of Activities

- Study participants who continue to receive study intervention after the DCO date (see Section 6.10) will be monitored and receive follow-up care in accordance with standard local clinical practice. Assessments will revert to the standard of care at a participant's study site and only SAEs, AEs leading to treatment/study discontinuation, overdoses, and pregnancies will be reported directly to the sponsor via paper forms (see Section 8.5.2).
- The SoA is presented in [Table 1](#).

Table 1 Schedule of Activities

	Screening	Intervention (treatment) Period								Safety Follow-up		Long Term Follow-up	Notes	
Assessment and Procedures	45 Day- to first dose	V1	V2	V3	V4	V5	V6	V7	Until PD	EOT	28 Days (±5 Days) After Last Treatment	12 Weeks (± 2 Weeks) After Last Treatment	Every 12 Weeks (± 2 Weeks)	D1: All assessments must be performed on day indicated (unless noted in assessment "Notes"). Day 15 through PD: Visits can be performed ±3 days. EOT: On day of or within 7 days of decision to discontinue. Follow up: Visits can be performed ±2 Weeks.
		W1	W3	W5	W7	W9	W11	W13						
		D1	D15	D29	D43	D57	D71	D85						
Informed consent	X													ICF can be signed up to 45 days before start of intervention.
Inclusion and exclusion criteria	X	X												Confirmation of all eligibility is required prior to dosing on W1D1. See SRM for more details
Demography	X													Sec Section 8.
Full physical examination (PE) including height	X	X	X	X	X	X	X	X	Q2W	X	X			Complete PE at Screening; Brief PEs should be performed at subsequent clinical visits and should include infusion site reaction assessments. Refer to Section 8.4.1. Height is required at screening only.
Weight	X	X	X	X	X	X	X	X	Q2W					Weight is required at every treatment visit.
Medical history (includes substance usage, CCI [REDACTED] CCI [REDACTED] within 60 days.)	X													Substances: alcohol and tobacco use, CCI [REDACTED] CCI [REDACTED] within 60 days prior to study intervention.
Disease Characteristics	X													Refer to Section 8.1
Prior anti-cancer drug/radiotherapy/procedures	X													

	Screening	Intervention (treatment) Period								Safety Follow-up		Long Term Follow-up	Notes	

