4.1. Overall Design

This is a Phase Ib open-label, global, multicenter, single-arm trial of bintralusp alfa administered to participants with metastatic or locally advanced/unresectable urothelial cancer with disease progression or recurrence following treatment with a platinum agent.

The primary study objective is to evaluate the objective response rate (ORR) per RECIST v1.1. Secondary objectives include evaluation of safety and tolerability of bintralusp alfa.

Participants who permanently discontinue study treatment will enter the follow-up period of the study and undergo the assessments as indicated in Section 8.

Approximately 25 participants will be treated in this study.

The study includes:

- 45-day screening period
- Treatment with bintralusp alfa 1200 mg as an IV infusion Q2W until disease progression as determined by the investigator using RECIST v1.1 [Eisenhauer, 2009] death, unacceptable toxicity, study withdrawal, or up to 2 years (see Section 7).
- Participants who have experienced a confirmed complete response (CR) can continue treatment for a maximum of 24 months after confirmation of response (at the discretion of the investigator). If the investigator believes that a participant with confirmed CR may benefit from treatment beyond 24 months, it may be permissible to continue treatment after discussion with the GSK medical monitor.
- Participants with SD or PR should continue treatment up to a period of 24 months from first dose until disease progression, or any other discontinuation criterion is met.
- Safety Follow-up: will continue until 12 weeks after the last dose of bintralusp alfa. The 12-week Safety Follow-up can be conducted via telephone calls or patient chart reviews unless there is medical necessity requiring a clinical visit.
- Long-term Follow-up: should be performed every 12 weeks after the Safety Follow-up according to the Schedule of Activities (SoA; see Table 1). Long-term Follow-up should be performed by chart reviews or telephone calls.
- Once the DCO date for the final analysis for this study has been reached, the clinical study database will be closed to new data and any participants that continue to receive study intervention at this time will be followed as described in Section 8.2.

Biopsies prior to study treatment are required, as described in eligibility criteria (Section 5.1). [REDACTED]

[REDACTED]

The overall study design is shown in the Study Schema [Figure 1]. A detailed SoA is located in Table 1.

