6.9. Intervention After the End of the Study

Study participants that continue to benefit from study intervention beyond the DCO date will continue to have access to study intervention until the EOS as defined in Section 4.7. There is no planned intervention following the EOS.

The investigator is responsible for ensuring that consideration has been given to the post-study care of the participant's medical condition.

Refer to the SoA (Table 1) for follow-up assessments of participants who are to be followed for disease progression and survival after they permanently discontinue from bintrafusp alfa until the DCO date and from the DCO date to the EOS.

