8.5.1. Time Period and Frequency for Collecting AE and SAE Information

All SAEs will be collected from the signing of the ICF at the time points specified in the [Table 1](#). Any SAEs assessed as related to study participation (e.g., study intervention, protocol-mandated procedures, invasive tests, or change in existing therapy) or related to a GSK product will be recorded from the time a participant consents to participate in the study.

All AEs will be collected from the signing of the ICF at the time points specified in [Table 1](#). Medical occurrences that begin before the start of study intervention but after obtaining informed consent will be recorded on the Medical History/Current Medical Conditions section of the case report form (CRF) not the AE section.

- All SAEs will be recorded and reported to the sponsor or designee immediately and under no circumstance should this exceed 24 hours, as indicated in [Appendix 3](#). The investigator will submit any updated SAE data to the sponsor within 24 hours of it being available.
- Investigators are not obligated to actively seek AEs or SAEs after the conclusion of the study participation. However, if the investigator learns of any SAE, including a death, at any time after a participant has been discharged from the study, and he/she considers the event to be reasonably related to the study intervention or study participation, the investigator must promptly notify the sponsor.

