8.5.2. Collection of Safety Information After Data Cut-off

After the DCO for the final analysis, in alignment with Section [6.10](#), participants still deriving benefit will continue to receive bintrafusp alfa. For these participants, GSK will continue to collect safety information, including SAEs, AEs leading to treatment/study discontinuation, overdoses, and pregnancy cases via paper forms (refer to the SRM) that will be submitted directly to GSK per defined time frames as follows:

- SAEs, AEs leading to treatment/study discontinuation, overdoses, and pregnancy cases will be reported until 35 days (5 half-lives) after last dose or the start of subsequent anti-cancer therapy, whichever comes first.
- An SAE will be followed until resolution unless the event is considered by the investigator to be unlikely to resolve, or the patient is lost to follow-up.

Reporting of these events (SAEs, AEs leading to discontinuation of study intervention, overdoses, and pregnancies) will continue to be in accordance with the protocol. The sponsor retains the right to request additional information for any participant with ongoing AE(s)/SAE(s) at the time of the DCO date for the final analyses, if judged necessary.

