### 9.1. DISPOSITION

Participant disposition and withdrawals (including those due to COVID-19), and reasons for exclusion from each analysis set, including inclusion and exclusion criteria will be presented for the SCR set.

The following information will be reported:

Document: [\\quintiles.net\\Enterprise\\Apps\\sasdata\\SAs\\sas\\GSK\\GSK4045154\\PZAA7715\\Biostatistics\\Documentation\\SAP\\GSK\\_213152\\_PZAA7715\\_SAP\\_Final\\_v1.0\\_07SEP2022](\\quintiles.net\\Enterprise\\Apps\\sasdata\\SAs\\sas\\GSK\\GSK4045154\\PZAA7715\\Biostatistics\\Documentation\\SAP\\GSK_213152_PZAA7715_SAP_Final_v1.0_07SEP2022)

Author: PPD [REDACTED] Version Number: 1.0

Version Date: 07SEP2022

Template No.: CS\_TP\_BS016 Revision 6 Reference: CS\_WI\_BS005

Effective Date: 02Dec2019

- Total number of participants screened (i.e. participants who gave informed consent)
- Number of participants who discontinued from the study prior to study treatment overall and grouped by the main reason (e.g. the failed specific inclusion or exclusion criteria, adverse event, lost to follow-up, protocol non-compliance, death, progressive disease, withdrawal by participant and other)
- Number of re-screened participants
- Number of participants who received at least one dose of study treatment (SAF)
- Number of participants with treatment ongoing at the data cut-off date
- Number of participants off study treatment, grouped by main reason (treatment completed as per protocol, adverse event, lost to follow-up, protocol non-compliance, death, progressive disease, withdrawal by participant and other)
- Number of participants ongoing on the study at the data cut-off date
- Number of participants who completed/discontinued the study participation, with the associated main primary reason (study completed according to protocol, adverse event, lost to follow-up, protocol non-compliance, death, progressive disease, withdrawal by participant and other).

No percentages will be provided for the number of participants screened and re-screened including for the reasons participants discontinued from the study prior to study treatment. All other counts will include percentages based on the number of participants in the SAF.

A participant will be considered to have completed the study if the participant dies or otherwise progresses during the treatment or follow-up period or has been in follow-up for a maximum of 3 years or if they are in follow-up when the DCO date is reached, whichever is sooner.

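### Participants who stopped drug within 35 days before the data cut-off get a shorter period of mandatory SAE reporting than those who continue, and the protocol conflicts on whether their 12-week safety follow-up goes on

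*Protocol*

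**What the plan says.** **Planned follow-up.** Table 1 (Protocol Section 1.3) schedules a safety visit "28 Days (±5 Days) After Last Treatment" and a contact at 12 weeks (±2 weeks). Section 4.1 says "Safety Follow-up: will continue until 12 weeks after the last dose of" the study drug, with no mention of the DCO. SAP Section 3.1 repeats this.

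**What Amendment 02 does at the DCO for participants already off drug.** The Synopsis has them "undergo the assessments as described in the SoA until the DCO date". The Protocol Summary says that at the final DCO "participants in follow-up will no longer be followed for survival and will be considered to have completed the study". Section 7.4 counts a participant as having completed the study once the DCO is reached in follow-up. SAP Section 9.1 does the same "if they are in follow-up when the DCO date is reached". The clinical database then takes no new data.

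**What continues after the DCO.** Section 8.5.2 describes participants who go on receiving the drug and then says "For these participants, GSK will continue to collect safety information". It covers SAEs, adverse events leading to discontinuation, overdoses and pregnancies, until 35 days (5 half-lives) after last dose or the start of other anti-cancer therapy. Section 8.2 limits its paper process to the same group. For anyone whose participation has ended, Section 8.5.1 says "Investigators are not obligated to actively seek AEs or SAEs after the conclusion of the study participation". What remains is a duty to notify SAEs that the investigator learns of and considers reasonably related.

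**A pointer the other way.** Section 6.9 sends sites to Table 1 for follow-up of participants off drug "until the DCO date and from the DCO date to the EOS" (end of study).

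**The concern.** By the protocol's own 35-day figure, a participant whose last dose was a week before the DCO is still inside the period in which SAEs are wanted from a continuing participant. Yet that participant is not in the continuing group, and on the Synopsis and Section 7.4 wording has no further scheduled contact. A participant dosed once more just after the DCO has every SAE reported for 35 days, or until other anti-cancer therapy starts.

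Two things are at stake. The first is safety capture: new SAEs in recent stoppers would reach the sponsor only if someone happens to hear of them and judges them related. The second is reading the tables. The SAP counts treatment-emergent adverse events (TEAEs) to last dose plus 30 days (Section 6.3.1) and tabulates deaths within 30 days of last dose (Section 14.2), with the treated set as denominator. A participant cut off inside that window stays in the denominator with part of the window unobserved. Safety is the secondary objective, and there are only 25 treated participants.

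**Working it through.** The plan states no figure to reproduce. The check traces the rules and then does date arithmetic.

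**Windows, W, in days after last dose**
- Safety visit: 28 (Table 1).
- 12-week safety follow-up: 12 × 7 = 84 (Table 1; Section 4.1).
- SAE reporting for continuing participants: 35 (Sections 8.2 and 8.5.2).
- TEAE window, and deaths after last dose: 30 (SAP Sections 6.3.1 and 14.2).

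**Formula.** For a last dose d days before the DCO, days falling after the DCO = max(0, W − d).

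| d | to 28-day visit | of 84 days | of 35 days | of 30 days |
|---|---|---|---|---|
| 7 | 21 | 77 | 28 | 23 |
| 14 | 14 | 70 | 21 | 16 |
| 27 | 1 | 57 | 8 | 3 |
| 60 | 0 | 24 | 0 | 0 |
| 84 or more | 0 | 0 | 0 | 0 |

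The visit allowances move the edges: 28 ± 5 gives days 23 to 33, and 84 ± 14 gives days 70 to 98. The 35-day and TEAE columns are upper limits, because both windows also end when other anti-cancer therapy starts.

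**Side by side, for d = 7**
- Synopsis and Section 7.4: assessments stop at the DCO and the participant has completed.
- Section 4.1 and SAP Section 3.1: safety follow-up runs to 12 weeks. The DCO bullet in the same list concerns only participants still receiving drug.
- Section 8.2: completion at the DCO is stated for participants in survival follow-up, which Table 1 keeps separate from safety follow-up.
- Section 6.9: follow up per Table 1 from the DCO to the end of study. Table 1 has no such schedule for someone already off drug; after the DCO it refers to Section 8.2.

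A site cannot obey all four.

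**What remains in force**
- Events already reported: the Synopsis and Section 8.5.4 follow SAEs and adverse events of interest to resolution or stabilization, with no DCO limit.
- New SAEs learned of and judged related: Section 8.5.1.
- Events ongoing at the DCO: the sponsor may ask for more information on any participant (Section 8.5.2).
- Pregnancies: Section 8.5.6 collects them to 2 months after last dose without naming the DCO.

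The loss is therefore scheduled contact and the active detection of new events.

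**The case against.** The strongest reply is that this is a drafting conflict and not a decision to drop anyone. Section 4.1 is current text and keeps 12 weeks of safety follow-up, Section 8.2 ends only survival follow-up, and Appendix 3 (Section 10.3.5) makes the paper form available for SAEs after the DCO without saying for whom. That stands to this extent: the text does not settle the matter, and a reporting channel exists. It does not remove the point, because no section obliges a site to use that channel for unrelated or unsought SAEs in a recent stopper.

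A second reply is that every cut-off analysis truncates. Participants still on drug are also analysed only to the cut-off (SAP Section 6.3.1). That stands too, so shortened table windows are not peculiar to this group; the difference in mandatory reporting is.

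A reader might infer more than the documents support:
- *That SAE information ceases altogether.* Follow-up of known events and notification of related SAEs continue.
- *That the TEAE and death proportions are biased downward.* They could be understated only if some participants have d below 30 and have events after the DCO. Last doses 30 to 84 days before the DCO leave both windows complete.
- *That a given share of the 25 is affected.* The documents give neither the DCO date nor the last-dose dates.
- *That recent stoppers are the likeliest to have late events.* Nothing in the documents shows this.
- *That Section 7.1 waives visits for this group.* Its statement concerns participants who stop after the DCO.

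**Conclusion.** The point holds as a gap in post-DCO reporting together with an internal conflict. A participant off drug with d below 35 loses up to 35 − d days of active SAE detection that a continuing participant keeps. With d below 84, the remaining 84 − d days of safety follow-up end under the Synopsis and Section 7.4 but continue under Section 4.1 and SAP Section 3.1. Only d below 30 touches the SAP's TEAE and 30-day-death windows, and there the proportions could be understated.

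The arithmetic assumes that the Synopsis rule is applied as written and that no other anti-cancer therapy starts inside the 35-day or TEAE window. The number affected lies anywhere from 0 to 25. It is zero if the DCO falls at least 84 days after the last dose of everyone who has stopped (98 days using the late edge of the 12-week contact). The change is cheap and worth making; the documents do not show that any planned result is wrong.

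**What to change.** 1. Reconcile the Synopsis and Protocol Sections 7.4, 8.2 and 8.5.2 with Sections 4.1 and 6.9 and SAP Section 3.1, so that one statement says whether safety follow-up already due continues past the DCO. Section 6.9 should point to a schedule that exists.
2. In Sections 8.2 and 8.5.2, extend the existing paper reporting to participants whose last dose was before the DCO but within the protocol's own 35 days, so that they are covered for the same period after last dose as participants still on drug.
3. In SAP Sections 9.1 and 14.2, report how many participants off drug had fewer than 30 days between last dose and the cut-off, so that the TEAE and 30-day-death proportions can be read with that in view. The completion category can stay as it is, since it agrees with Protocol Section 7.4.

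The cost is amendment wording, some paperwork at sites for what may be a few participants or none, and one count in the SAP. Items 2 and 3 do different jobs: reports sent to the pharmacovigilance database improve safety capture but do not alter tables from the locked clinical database, so only the count helps a reader of those tables.
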